7.6 Follow-up for Adverse Events

Any SAEs related study participation will be followed for outcome information until resolution or stabilization. Follow-up reports will be submitted to the IRB, SMC, or NCCIH as required in each specific instance.

7.7 Safety Monitoring

The NCCIH requires that all Human Subjects research studies undergo independent monitoring, and NCCIH Program Officials will provide specific guidelines to the PI for the study.

8. INTERVENTION DISCONTINUATION

Prisoners will be discontinued from an intervention in the following circumstances:

- If the prisoner or prison staff does not believe it is in the best interest of the prisoner to continue. As soon as an MPI is informed of this, study staff will speak with the participant about discontinuation, if possible.
- If a prisoner chooses to discontinue attendance.
- If one of the MPIs, in consultation with the relevant instructor, finds the prisoner to be so disruptive to the rest of the class that he/she has a repeated and substantive negative impact on the other participants.
- If a prisoner is released from prison unexpectedly.
- If a prisoner exhibits inappropriate behavior towards study staff.

Participants will continue with subsequent assessments if they are willing to do so. Assessment schedule and assessments used will not change.

9. STATISTICAL CONSIDERATIONS

9.1 General Design Issues

For this pilot treatment development trial, assessment of feasibility, acceptability, and safety of the intervention and research procedures is the primary goal. Nonetheless, pilot data can be used to demonstrate whether the effects of treatment look promising across a set of outcome variables, to begin to examine the distribution of outcome variables to inform future analytic strategies, and to suggest, in concert with results from larger scale clinical trials in related fields, the range of effect sizes that would be reasonable to expect in a future trial.

Because this is a treatment development study, we have chosen our sample sizes as being sufficient to assess feasibility and acceptability. This study is not powered to assess differences between treatments.

9.1.1. Summary of Aims, Endpoints, and Data Analytic Strategy.

Table 5 summarizes each aim, the target endpoint, and the data analysis strategy, where applicable.

Table 5. Summary of Aims, endpoints, and analyses.

Aim/ Objective	Endpoint	Analyses
Phase 1 – Focus Groups		
To conduct focus groups with prisoners and criminal justice stakeholder groups (separately) to understand ways of increasing feasibility, acceptability, and efficacy of yoga for anger management as well as feasibility and acceptability of our control arm (health education);	Conduct 4 focus groups, composed of approximately 6 individuals each.	Qualitative analysis – see description below.
To solicit feedback from experts in correctional mental health, addiction, and yoga	Feedback received from experts in relevant areas	Qualitative analysis- see description below.
To modify our existing yoga treatment manual, health education manual, and instructor fidelity scales.	Draft of yoga manual, health education manual, and instructor fidelity scales	N/A
Phase 2 – Pilot RCT		
To conduct a pilot RCT of hatha yoga vs. health education	40 prisoners enrolled & follow up assessments completed	N/A
To assess feasibility and acceptability of both the yoga class and the health education control group. ** This is primary.**	See Table 6 for a complete list	Descriptive statistics (see Table 6) and qualitative data analysis
To assess safety, we will track all adverse events in a structured fashion.	See Table 6 for a complete list	Descriptive statistics (see Table 6)
To assess feasibility of research procedures,	See Table 6 for a complete list	Descriptive statistics (see Table 6)
To assess within-group changes on outcomes. The primary clinical target (and primary outcome for a subsequent efficacy trial) will be anger dysregulation assessed by the NAS at post-intervention (wk10). Secondary targets (and secondary outcomes for a subsequent efficacy trial) include Aggression (AQ-SF); behavioral infractions, depression (PHQ-9), anxiety (PROMIS Anxiety), and functional impairment (SF-12). We will assess these changes from pre-intervention to post-intervention (wk10), and pre-intervention to follow-up (wk18). ** This is exploratory.**	Endpoint = post-intervention (wk10); follow-up (wk18)	Within-subjects t-tests (e.g., from pre-intervention to post-intervention/wk10, and pre-intervention to wk18). We will conduct analyses separately by treatment group. We will calculate effect sizes (Cohen's d) from pre- to post- treatment/wk10, with corresponding confidence intervals.
Assess within-group changes on anger rumination, decentering, and impulsivity. ** This is exploratory.**	Endpoint = post-intervention (wk10).	Within-subjects t-tests (e.g., from pre-intervention to wk10). We will conduct analyses separately by treatment group.

9.1.2. Description of Assessment Instruments.

All interview and self-report assessment measures were chosen because they have strong psychometric properties for measurement of constructs of interest to the study, and have been used in other NIH-funded clinical trials and prospective studies. With signed releases of information (ROIs) obtained at the baseline assessment, we will supplement interview and self-report data with criminal justice records review to assess for rates of behavioral infractions in prison.

Acceptability and Feasibility. Intervention credibility and patient expectations for intervention success at baseline will be measured with the Credibility Expectancy Questionnaire (CEQ)²³; this is administered after their initial class. The Client Satisfaction Questionnaire (CSQ-8)²⁴ will be used post-treatment to assess satisfaction with treatment. We will also use qualitative responses to a detailed post-treatment interview to gain participants' feedback about intervention components and research procedures. Finally, it is critical that the amount of yoga practice at home be measured as accurately as possible. Participants will complete a yoga homework questionnaire on a weekly basis. The tool will yield three indices of home practice: frequency of extended home practice, minutes of extended home practice, and frequency of micro home practice.

Participant safety. After each homework questionnaire, we will ask participants in the yoga arm only whether they experienced any injuries as a result of yoga practice. At each follow-up, we will administer the Systematic Assessment of Treatment-Emergent Events – General Inquiry (SAFTEE)²⁵ to all participants. This allows us to systematically assess number of adverse events, severity, and resulting impairment. Finally, any time a participant reports an adverse event to any staff member, a research assistant will talk with the participant to ascertain information for recording of the adverse event. For adverse events ascertained by any of these three possible methods, the research assistant gets information on what happened, start and stop dates, severity, functional impact, interactions with healthcare professionals, perceived cause, and possible relation to study participation. For more information and details on coding of AEs, please see DSMP.

Anger and aggression. We will use the two-part Novaco Anger Scale and Provocation Inventory (NAS-PI)^{26,27} to measure anger. The first part of the measure, the Novaco Anger Scale (NAS) will be used to measure the primary outcome of anger dysregulation. The NAS is a 48-item scale that yields a total score reflecting the likelihood and severity of experiencing anger reactions across cognitive, arousal, and behavioral, domains of anger. Each of these domains has a corresponding subscale that can be evaluated separately. The Novaco Provocation Inventory (PI), contains 25 items that assess anger reactivity to a variety of provocations (e.g., annoyances, disrespect, frustration, perceived injustice). This will be a secondary outcome. The NAS-PI is among the most widely used measures of anger,²⁸ and has demonstrated strong reliability and validity (including concurrent validity with other measures of anger,²⁹⁻³²) across many different samples,³³⁻³⁵ including incarcerated^{30-32,36} and other CJ-involved³⁶⁻³⁸ individuals. To measure aggression, we will use the Aggression Questionnaire-Short Form (AQ-SF).^{39,40} The AQ-SF is a widely used scale that measures self-reported physical and verbal aggression. It has been validated for use across range of populations,^{40,41} including those who are CJ-involved.^{42,43} Finally, we will assess frequency of behavioral infractions in prison, and receipt of disciplinary action through review of local criminal justice records, as well as through self-report.

Other Secondary Outcomes. The Patient Health Questionnaire (PHQ-9)⁴⁴ will be used to assess depression via self-report. The PHQ-9 has established reliability and validity. We will use the self-report PROMIS anxiety⁴⁵ 8-item scale (short form 8A) to assess , anxiety severity. Functional impairment will be assessed via the SF-12,⁴⁶ a brief, widely used self-report measure

of physical and mental health functioning.

Potential Mechanisms of Action. The Anger Rumination Scale (ARS)^{47,48} is a 19-item self-report questionnaire that measures the tendency to focus and perseverate on angry affect and past anger experiences. Unlike the cognitive subscale of the NAS, this scale measures a cognitive process, rather than the content of cognitions, *per se*. We will use the Experiences Questionnaire (EQ)^{49,50} to assess decentering. Decentering is a process of distancing from and observing cognitive content, without judgment or reactivity.⁵¹ The EQ consists of 20 items and two subscales: decentering and rumination. Finally, the Stroop Color Word Test⁵²⁻⁵⁴ will be administered as a task-based measure of disinhibition and impulsivity.

Other Measures. Subjects will be asked for demographic information and, number of prior arrests and incarcerations, and length of time spent incarcerated. **For purposes of determining inclusion/ exclusion criteria**, the mood and psychosis modules of the brief MINI Neuropsychiatric Interview⁵⁵ will be used to assess for current mania, psychosis, or active suicide risk (see section 4.7.1). The Physical Activity Readiness Questionnaire⁵⁶ (PAR-Q) will be used to determine whether a participant is able to safely engage in a moderate level of physical activity. As noted in section 4.7.1, if someone answers “yes” to any of the 7 items on the scale they will be ruled ineligible for the study. **For descriptive purposes**, the Life Events Checklist/PTSD Checklist^{57,58} (LEC/PCL) will be used to assess for lifetime history of trauma exposure and severity of PTSD symptoms. The Treatment History Interview⁵⁹ (THI) will be used to assess mental health treatment (i.e., pharmacotherapy, psychotherapy, group therapy, 12-step participation) received over the course of study participation. Finally, we will use the International Physical Activity Questionnaire²² (IPAQ), a self-report measure of physical activity. We have adapted this scale to measure amount of yoga practice engaged in during the follow-up time period, as well as other physical activity. The Qualitative Interview - Intersectional Stigma (for yoga participants only) will be conducted to assess intersectional stigma or multilevel resiliency in the context of incarceration among people participating in a yoga program.

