Phase 1 (Focus Group) Exclusion Criteria – Stakeholders

None.

4.3 Inclusion and Exclusion Criteria, Prisoners, Phase 2.

Participants must meet all of the relevant inclusion criteria to participate in the study.

Phase 2 Inclusion Criteria – Prisoners

1. Age 18-70;
2. Clinically significant anger dysregulation, as evidenced by a score ≥ 86 on the Novaco Anger Scale (NAS);
3. Prisoner or jail detainee, with anticipated duration of remaining time incarcerated of 90 days or more, allowing for participation in the 10 week intervention;
4. Ability and willingness to provide informed consent; and
5. Willingness to be audio recorded in the intervention condition sessions (e.g., yoga or health education groups).

Phase 2 Exclusion Criteria – Prisoners

1. Presence of current manic or psychotic symptoms, or suicide risk (warranting referral to prison mental health clinical staff);
2. Any endorsed item on the Physical Activity Readiness Questionnaire (PAR-Q) except for item 6 (i.e., participants can be included even if they endorse item 6);
3. Current weekly yoga practice or current participation in mindfulness- based programming;
4. Pregnancy; and
5. Inability to understand English sufficiently well to understand the consent form or assessment instruments when read aloud.

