6. STUDY PROCEDURES

6.1 Schedule of Evaluations

Table 1. Schedule of Evaluations, Phase 1, Prisoners.

Assessment	Baseline and Enrollment: (Day-30 to Day -1)	Focus Group Visit 1 (Day 0)
Inclusion/ Exclusion	X	
Informed consent form	X	
Demographics	X	
Novaco Anger Scale – Provocation Inventory	X	
MINI (screening)	X	
Physical Activity Readiness Questionnaire	X	
Payment		\$20

Table 2. Schedule of Evaluations, Phase 1, Stakeholders.

Assessment	Baseline and Enrollment: (Day-30 to Day -1)	Baseline, Enrollment, Visit 1 (Day 0)
Inclusion/ Exclusion	X	
Informed consent form		X
Demographics		X
Payment		\$20

Table 3. Schedule of Evaluations, Phase 2.

Assessment	Type of Assessment	Baseline1, Visit 1 (Day 0)	After initial class	After each class	Wk 5	Wk 10	Wk 14	Wk 18
Inclusion/ Exclusion	Interview, pre-randomize	X						
Informed Consent Form	Pre-randomize	X						
Enrollment/ Randomization	Interview	X						
CEQ	Self-report		X					
CSQ-8	Self-report					X		
Qualitative Interview	Interview					X	X (yoga only)	
Homework Questionnaire	Self-report			X				
Injuries due to yoga	Self-report			X				
SAFTEE- GI	Interview	X			X	X		X
Novaco Anger Scale- Provocation Inventory	Self-report	X			X	X		X
Aggression Questionnaire- Short Form	Self-report	X			X	X		X
Behavioral Infractions in Prison	Record Review	X			X	X		X
Patient Health Questionnaire-9	Self-report	X			X	X		X
PROMIS Anxiety	Self-report	X			X	X		X
SF-12 from RAND Medical Outcomes Study	Self-report	X			X	X		X
Anger Rumination Scale	Self-report	X			X	X		X
Experiences Questionnaire	Self-report	X			X	X		X
Stroop Color and Word Test	Task	X			X	X		X
MINI (screening)	Interview	X						

Assessment	Type of Assessment	Baseline1, Visit 1 (Day 0)	After initial class	After each class	Wk 5	Wk 10	Wk 14	Wk 18
Physical Activity Readiness Questionnaire	Self-report	X						
Life Events Checklist/PTSD Checklist	Self-report	X						
Treatment History Interview	Interview	X			X	X		X
International Physical Activity Questionnaire	Self-report	X			X	X		X
Payment					\$20	\$20	\$20	\$20

Abbreviations: timepoints: Wk5, Wk10, Wk18 = Week 5, Week 10, Week 18.

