9.3 Definition of Populations

All data analysis will use the intent to treat population and use all available data. There is no per protocol analysis planned.

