Feasibility and Acceptability—Research Procedures	
Recruitment rate	Average of 6 enrolled per month
Retention rate	80% complete week 10 assessment; 70% complete wk. 18 assessment
Completion of items on assessment instruments	At least 90% of items are completed on each assessment instrument (so each will be valid).

9.5.2 Secondary/ Exploratory Outcomes.

In Phase 2, we will also examine change in key variables over time. This is an exploratory analysis.

Specifically, we will look at change over time the in the following variables. The primary outcome in a subsequent efficacy study is in **bold and underlined**. Secondary outcomes are in standard text. *Potential mechanisms are in italics*.

- **NAS-Provocation Inventory from BL to wk10**; BL to wk18.
- Aggression Questionnaire – Short Form, BL to wk10; BL to wk18.
- Number of behavioral infractions in Prison, BL to wk10; BL to wk18
- PHQ-9, BL to wk10; BL to wk18
- PROMIS Anxiety, BL to wk10; BL to wk18
- SF-12 physical health composite score, BL to wk10; BL to wk18
- SF-12 mental health composite score, BL to wk10; BL to wk18
- *Anger rumination scale, BL to wk10; BL to wk18*
- *Experiences Questionnaire, BL to wk10; BL to wk18*

- *Stroop Color and Word Test, BL to wk10; BL to wk18*

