If the minority distribution of our participants falls below the targeted minority distribution (i.e., if halfway through the study, the proportions of African Americans or Hispanics recruited are less than two thirds of the proportion of that minority distribution for the RIDOC), then we will conduct additional outreach to the group that fell below their targeted enrollment numbers. We will also attempt to obtain feedback on why individuals for that group may refuse to participate in the study. Based on the feedback, we will take corrective action. All subjects will be asked to identify their race and ethnicity separately, by self-report, at the time of study entry, when demographic information is collected. We plan to conduct analysis to determine whether minority status is associated with any of the treatment utilization or clinical outcome data collected as part of this investigation. The Targeted/Planned Enrollment Table displays the expected racial and ethnic distribution of participants for this study.

Inclusion of Children. Individuals aged 18-21 who meet our inclusion criteria will be included in this study. Individuals younger than 18 will not be included. Stakeholder focus group participants will be employees of the RIDOC, and therefore over the age of 18. However, children 18-21 will be included. This study will not include anyone under 18 years of age (the age of emancipation in Rhode Island) because individuals younger than age 18 are supervised by the RI Juvenile Corrections Division (not the RIDOC) and because adolescent developmental issues would confound outcomes of interest to the study and because incarcerated individuals. Additional instruments and study methods would also be required to assess the unique mental health needs of a younger population. Thus, the current research is not applicable to children under the age of 18.

Because children ages 18-21 are of legal age, they will be treated as adults and will be able to consent and agree to participate in the study themselves. Our consent procedures are conducted face-to-face, with trained interviewers guiding eligible subjects step-by-step; materials are written at a Grade 7 level and the interviewers ensure that each element is understood. In addition, consent forms will be read aloud.

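### Table 5 judges the impulsivity mechanism by within-arm change on a repeated Stroop task, which cannot separate the intervention from practice or time; section 9.6 already plans a between-group comparison, and the two should be aligned

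*Combined protocol and SAP*

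**What the plan says.** Protocol section 9.1.1, Table 5, last row, gives the aim as "Assess within-group changes on anger rumination, decentering, and impulsivity", marks it exploratory, sets the endpoint at week 10, and specifies "Within-subjects t-tests (e.g., from pre-intervention to wk10). We will conduct analyses separately by treatment group". Unlike the row above it, which covers the clinical outcomes, this row asks for no effect size or confidence interval.

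Section 9.1.2 names one impulsivity measure, the Stroop, which "will be administered as a task-based measure of disinhibition and impulsivity". In section 6.1, Table 3, the row "Stroop Color and Word Test" is marked at baseline and weeks 5, 10 and 18. Section 9.5.2 lists "Stroop Color and Word Test, BL to wk10; BL to wk18" among the potential mechanisms. No section says which Stroop score is used, whether alternate forms are used, or how practice is handled.

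Section 9.6 plans a repeated-measures ANOVA across time points for key variables, among them the possible mechanisms. It adds effect sizes for differences between groups at each time point, with 95% confidence intervals.

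On who may do the task, the Phase 2 language exclusion in section 4.3 is "Inability to understand English sufficiently well to understand the consent form or assessment instruments when read aloud", and section 11.5 adds "In addition, consent forms will be read aloud". No reading criterion is listed. Section 9.3 states "All data analysis will use the intent to treat population and use all available data".

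**The concern.** Performance on a repeated task can improve because it has been done before. By week 10 each participant is due to have taken the Stroop three times, and by week 18 four times. A paired test within one arm asks only whether the mean moved, and it attributes to a single number whatever the intervention, repetition and ten weeks in custody have each contributed. The trial has a randomised control arm on the same Stroop schedule, which would remove any practice gain common to both arms, but the row that states this aim does not use it.

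Section 9.1 says that pilot data can show whether effects look promising and can suggest plausible effect sizes for a future trial. A practice gain read as a change in impulsivity could therefore affect which mechanism and which measure are carried forward.

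A second, smaller issue is validity. Questionnaires can be read to a participant. A task built on printed words cannot be replaced in that way, and the plan does not say how to treat someone who cannot do it properly.

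**Working it through.** The plan states no power, test level, effect size or practice effect for the Stroop, so there is no figure of its own to reproduce.

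**Inputs from the documents**
- 40 randomised (protocol 9.2.1), 1:1 (Data Safety Monitoring Plan 7.2): 20 per arm.
- Retention target of 80% at week 10 (target outcomes table, 9.5.1): 0.80 × 20 = 16 per arm.
- Stroop at baseline, week 5 and week 10 (Table 3): three administrations by the endpoint.

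**Assumptions (not in the documents)**
- Two-sided test level of 5%; the plan mentions only 95% intervals.
- Practice gain d by week 10 of 0.1, 0.2 or 0.3 baseline SD, equal in both arms.
- Retest correlation r of 0.7 to 0.8.
- No intervention effect.

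**Step 1. Within-arm test.** The SD of change, in baseline SD units, is √(2(1−r)): 0.775 at r = 0.7 and 0.632 at r = 0.8. The standardised change is dz = d/√(2(1−r)), and the noncentrality is dz × √16. The critical value is t(0.975, 15 df) = 2.131. For d = 0.2 and r = 0.7, dz = 0.2/0.775 = 0.258, the noncentrality is 1.033 and the rejection probability is 0.162.

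| Assumed gain | One arm, r = 0.7 | One arm, r = 0.8 | At least one arm |
|---|---|---|---|
| 0.1 SD | 7.7% | 9.1% | 15–17% |
| 0.2 SD | 16.2% | 22.0% | 30–39% |
| 0.3 SD | 30.6% | 42.7% | 52–67% |

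The last column is 1 − (1 − p)², treating the arms as independent. With no practice gain it would be 1 − 0.95² = 9.8%.

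**Step 2. Between-arm contrast.** An equal gain in both arms drops out of the difference. In 40,000 simulated trials per setting, with gains of 0 to 0.5 SD of change and 20 or 16 per arm, a between-arm test of change rejected 4.8–5.3% of the time.

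**Step 3. Price in precision.** At 16 per arm, the 95% half-width of a within-arm mean change is 2.131/√16 = 0.53 SD of change. For a between-arm difference in change it is 2.042 × √(2/16) = 0.72 SD of change. Baseline adjustment multiplies the residual variance of that difference by (1 − r²)/(2(1 − r)) = (1 + r)/2, which is 0.85 to 0.90 here, so the adjusted interval is slightly narrower than 0.72.

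**Step 4. Reading.** A stable reading level adds the same amount to a person's baseline and week-10 scores and cancels in the change. The simulations in step 2 included such a component: at 20 per arm and a gain of 0.3 SD of change, the within-arm test rejected 25.0% of the time, against 24.7% by formula without it. If a share f of participants cannot show change on the task, a true mean change shrinks to (1 − f) of its size: 0.9, 0.8 or 0.7 for assumed f of 10%, 20% or 30%.

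**The case against.** The strongest reply is that the comparison already exists. Section 9.6 is the data-analysis section, it names the possible mechanisms, and it plans between-group effect sizes with 95% intervals at each time point, where equal practice cancels. Table 5 is introduced as a summary, and nothing says it overrides section 9.6. This largely stands: a reader who saw only Table 5 might infer that the plan has no between-arm comparison of the Stroop, and that would be wrong. What remains is that the section 9.6 contrasts are not stated to be adjusted for baseline, and that Table 5 still gives this aim the non-comparative test.

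A reader might also infer that the test measures reading ability rather than impulsivity. The documents do not support that, and step 4 shows that stable reading ability cancels in a within-person change. It could bias the change only if reading altered the size of the practice gain or improved during the study.

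Nor can one say that the pilot is likely to report improved impulsivity when nothing has changed. The chance for at least one arm passes one half only at an assumed gain of about 0.3 SD; at 0.2 SD it is 30–39%. The plan names no Stroop score, so its sensitivity to practice cannot be settled from the documents.

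Finally, the row is exploratory, the trial claims no power for treatment differences, section 9.6 concedes that its intervals may not permit firm conclusions, and no Stroop result is among the target outcomes that bear on whether a larger trial is proposed. All of that stands and limits the severity. The plan's 90% item-completion target and its checks for outliers and missing data are useful but do not identify someone who cannot read the words.

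**Conclusion.** The point holds in a limited form. The test that Table 5 assigns to impulsivity cannot separate intervention from practice or time, and Table 5 and section 9.6 describe different analyses for the same aim. Under an assumed practice gain of 0.1 to 0.3 SD, r of 0.7 to 0.8 and 16 per arm, the nominal 5% per-arm error becomes roughly 8% to 43%; with no practice gain or time trend it stays at 5%. These figures show what practice could do; they are not an estimate of what it will do. The absence of a reading criterion is a validity issue that may dilute a true change in proportion to an unknown share of participants; it does not manufacture one. Severity is low because the analysis is exploratory, but the correction costs little.

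**What to change.** In Table 5 and section 9.5.2, define the Stroop analysis as the between-arm difference at week 10, adjusted for baseline Stroop score and facility stratum, with a 95% confidence interval, and word it to agree with section 9.6. Report within-arm change descriptively only, labelled as including practice and time effects. Name the Stroop score to be analysed.

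Record at baseline whether the participant can read the printed words, and report the number who cannot by arm. Keep all records in the main analysis, in line with section 9.3, and add a sensitivity analysis without those participants.

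The cost is a few sentences of analysis text, one extra form field, and a wider interval than the within-arm one (about 0.72 against 0.53 SD of change at 16 per arm, before baseline adjustment). No visit or staff is added.
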